10.4 Statistical Methods

Analysis will include summaries of data collected in this OLE study as well as integrated OLE data and repeat dosing data collected in WVE-HDSNP1-001.

10.4.1 Study Drug Exposure and Compliance

The extent of study drug exposure and compliance will be summarized by dose group for the safety population.

10.4.2 Analysis of Safety Data

The summary of safety results will be presented by dose group. All safety analyses will be performed on the safety population using the following common rules:

- The OLE baseline value is defined generally as the last available value from WVE-HDSNP1-001 before first dose in WVE-HDSNP1-002.
- The repeat dosing baseline value is defined generally as the last available value before initiation of repeat dosing. Initiation of repeat dosing can occur in either WVE-HDSNP1-001 or WVE-HDSNP1-002.
- Adverse event observation periods are defined as follows:
 - Pre-OLE treatment AEs are AEs that developed or worsened between the date of signed informed consent for the OLE and the date of first dose of study drug in the OLE.
 - OLE on-treatment adverse events are AEs that developed or worsened from the first dose of study drug in the OLE to study completion/discontinuation. Summaries of TEAEs will include all OLE on-treatment AEs.
 - Repeat dosing on-treatment adverse events are AEs that developed or worsened from the first dose of repeat dosing to study completion/discontinuation. Initiation of repeat dosing can occur in either WVE-HDSNP1-001 or WVE-HDSNP1-002. Summaries of repeat dosing TEAEs will include all repeat dosing on-treatment AEs.
- For quantitative safety parameters based on central laboratory/reading measurement descriptive statistics will be used to summarize results and change from baseline values by visit and dose group.

Adverse Events

Treatment-emergent AEs, treatment-emergent SAEs, and TEAEs leading to treatment discontinuation will be summarized by dose group based on Medical Dictionary for Regulatory Activities (MedDRA) coding of verbatim terms reported by investigators.

Adverse event incidence tables will present, by system organ class (SOC) and preferred term, the number and percentage of patients experiencing an AE. Multiple occurrences of the same event will be counted once in the tables. The denominator for computation of percentages is the safety population within each dose group.

Adverse event incidence tables will present, by SOC and preferred term, the number and percentage of patients experiencing an AE by severity and by relationship to treatment. In tabulating the severity of adverse events, the highest severity will be assigned to a subject with more than one occurrence of the same adverse event. The highest level of association will be reported in subjects with differing relationships for the same adverse event.

Similar tables will be generated summarizing repeat dosing TEAEs. Listings of all AEs, SAEs, deaths, and AEs leading to study discontinuation will be provided.

Clinical Laboratory Evaluations

Summary statistics of laboratory variables including CSF safety laboratory variables will be calculated for each visit or study assessment by dose group. Laboratory data will also be categorized as low, normal, or high based on the reference ranges of the central laboratory. Frequencies and percentages will be presented by dose group for the shifts in these categories from baseline to post-baseline assessment time points. A listing of clinically significant hematology and chemistry findings will be provided.

Other Safety Evaluations

Summary statistics of vital signs, ECG, and height and weight variables will be calculated for each visit or study assessment by dose group.

Columbia-Suicide Severity Rating Scale

Listings of patients who respond “yes” to item 4 or 5 on the C-SSRS at any point in the study will be provided.

Immunogenicity

Anti-drug antibody assay results to WVE-120101 will be described categorically. Summary statistics for anti-drug antibody titer results will be provided.

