5.2 Exclusion Criteria

1. Clinically significant medical finding on the physical examination other than HD that, in the judgment of the Investigator, will make the patient unsuitable for participation in and/or completion of the study procedures.
 2. Received an investigational drug other than WVE-120101, including an investigational oligonucleotide, within the past 1 year or 5 half-lives of the drug, whichever is longer.
 3. Implantable CNS device that may interfere with ability to administer study drug via lumbar puncture or undergo MRI scan.
 4. Diagnostic and Statistical Manual of Mental Disorders 5th Edition (DSM-5) diagnosis at the Screening Visit of active alcohol, cannabinoid, or other substance use disorder (except nicotine).
 5. Positive for opioids (unprescribed), cocaine, amphetamines, methadone, barbiturates, methamphetamine, or phencyclidine at the Screening Visit.
 6. Pregnant (as determined by a serum pregnancy test) or breast feeding at the Screening Visit, or plans to become pregnant during the course of the study.
-

7. Clinically significant laboratory abnormality at Screening, including, but not limited to:
 - a. Alanine aminotransferase (ALT) or aspartate aminotransferase (AST) values at Screening or Baseline >3 times the upper limit of normal (ULN).
 - b. Renal insufficiency, defined as either serum creatinine >1.8 mg/dL or creatinine clearance <40 mL/min.
8. Clinically significant abnormality at Screening electrocardiogram (ECG), including but not limited to a confirmed QT interval corrected for heart rate (QTc) ≥ 450 msec for males or ≥ 470 msec for females.
9. Clinically significant cardiovascular, endocrine, hepatic, renal, pulmonary, gastrointestinal, neurologic, malignant, metabolic, psychiatric, or other condition that, in the opinion of the Investigator, precludes the patient's safe participation in the study or would interfere with the study assessments.
10. Bone, spine, bleeding, or other disorder that exposes the patient to risk of injury or unsuccessful lumbar puncture.
11. Inability to undergo brain MRI (with or without sedation).
12. In the opinion of the Investigator, deemed to be at significant risk for suicidal behavior

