8.1.5 Height and Weight

The patient's height and weight will be measured at the time points described in the Schedule of Assessments (Section 4.2) and recorded in the eCRF and source documents.

8.1.6 12-Lead ECG

Computerized, good quality, 12-lead ECGs will be recorded in triplicate at the time points described in the Schedule of Assessments (Section 4.2). Recordings will be obtained in the supine position after the patient has rested comfortably for ≥ 5 minutes.

The ECG tracing will be submitted and read by a centralized reviewer (details will be provided in the ERT[®] Study Manual). The following should be recorded on the trace and eCRF: whether the ECG is normal or abnormal and, if deemed abnormal, whether the abnormality is clinically significant or not clinically significant, with the abnormality noted.

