8.1.7 Clinical Laboratory Evaluations

Clinical laboratory safety testing will be collected at the time points described in the Schedule of Assessments (Section 4.2) and recorded in the eCRF and source documents. A blood sample will be tested locally up to 1 week prior to the lumbar puncture to determine platelet count and prothrombin time, and thereby confirm that it is safe to proceed with the lumbar puncture. Other safety laboratory samples will be analyzed at a central laboratory. Local testing on these samples may be conducted as clinically indicated.

The parameters to be assessed are presented in Table 3.

Table 3 Clinical Laboratory Parameters

Hematology	Coagulation	Clinical chemistry	Urine dipstick
Complete blood count, including: 
 • White blood cell count (with differential) • Red blood cell count • Hemoglobin • Hematocrit • Platelet count • Reticulocyte count • Mean corpuscular volume • Mean corpuscular hemoglobin • Mean corpuscular hemoglobin concentration Measures of Inflammation, including: 
 • High Sensitivity C-reactive protein • Complement 	Activated partial thromboplastin time Prothrombin time Fibrinogen	Sodium Potassium Chloride Bicarbonate Blood urea nitrogen Creatinine Creatine phosphokinase Alanine aminotransferase Aspartate aminotransferase Alkaline phosphatase Bilirubin	Urinalysis

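### Read literally, Section 10.4.2 takes the OLE baseline from the parent study, so laboratory movement before the first OLE dose can be counted as post-baseline change

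*Combined protocol and SAP*

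**What the plan says.** Section 10.4.2 lists common rules for all safety analyses. Two of them define baselines:

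- OLE baseline: "The OLE baseline value is defined generally as the last available value from WVE-HDSNP1-001 before first dose in WVE-HDSNP1-002".
- Repeat-dosing baseline: "The repeat dosing baseline value is defined generally as the last available value before initiation of repeat dosing". The text adds that repeat dosing may begin in either study, so this definition is not tied to one of them.

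The same section then uses a baseline in two kinds of summary:

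- "For quantitative safety parameters based on central laboratory/reading measurement descriptive statistics will be used to summarize results and change from baseline values". These are given per dose group at each visit.
- For laboratory data, "Laboratory data will also be categorized as low, normal, or high based on the reference ranges of the central laboratory", and then "Frequencies and percentages will be presented by dose group for the shifts in these categories from baseline to post-baseline assessment time points".

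Neither summary says which of the two baselines it means.

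On data collection, Table 1 (Section 4.2) marks clinical laboratory evaluations at Screening and at Week 1. Footnote f lets the dosing-visit sample be taken up to 1 week ahead. Apart from the local platelet count and prothrombin time before lumbar puncture, Section 8.1.7 says: "Other safety laboratory samples will be analyzed at a central laboratory". Table 1 also has an ECG at Screening, and Section 8.1.6 says: "The ECG tracing will be submitted and read by a centralized reviewer". Footnote a and Section 4.1.1 allow final parent-study values to stand in at Screening if they fall within 4 weeks of it.

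**The concern.** A baseline for an extension study should normally be the most recent value before the first extension dose. The OLE bullet instead names the parent study as the source, although the OLE collects newer values before dosing. A programmer who follows the sentence would pass over the Week 1 laboratory sample, and also any fresh Screening sample, in favour of an older one.

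Safety is the primary objective, and laboratory change and shift tables are part of how it is described. If a value moved between the studies and stayed there, these tables would show a change after OLE baseline even though nothing moved after the first OLE dose. The adverse event rules in the same list do split time at the first OLE dose, so the laboratory tables and the event tables would use different starting points.

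**Working it through.** The plan states no figure to reproduce. The check compares the wording with the schedule and then does the arithmetic that follows.

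**1. Which measures are caught.** The change-from-baseline rule covers centrally analysed or centrally read measures.

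- Clinical laboratory tests: central, with OLE values at Screening and Week 1 before the first dose. Caught by both the change and the shift summaries.
- ECG: centrally read. Screening is the only OLE ECG before the first dose, and no ECG shift table is planned. Footnote a is on the Screening column heading but not on the ECG row, so a parent ECG may be allowed to stand in. Caught for change only, and only if a new Screening ECG was done.
- CSF safety tests (local) and weight (by-visit statistics only): not clearly caught.

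**2. Age of the baseline at the first OLE dose.**

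- Parent value reused at Screening: up to 4 weeks before Screening, plus up to 4 weeks of Screening (Day -28) = 8 weeks.
- Parent value not reused at Screening: no maximum interval between the studies is stated.
- Week 1 laboratory sample: at most 1 week. The avoidable age in the reuse case is therefore up to 8 - 1 = 7 weeks, or 8 weeks if the sample is taken on Day 1.
- New OLE Screening ECG: at most 28 days = 4 weeks.

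**3. Effect on change from baseline.** Let P be the last parent value, W the last value before the first OLE dose, and Y a later value. Then

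Y - P = (Y - W) + (W - P).

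The term W - P is movement before the first OLE dose. It enters change from OLE baseline one for one, and disappears if W is the baseline.

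**4. Example with assumed values.** ALT is 0.8 x ULN at the last parent visit, 2.0 x ULN at Week 1 before dosing and 2.0 x ULN at Week 5. This is under the 3 x ULN limit in exclusion 7a and is assumed not to be judged clinically significant.

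- Baseline as written: 2.0 - 0.8 = +1.2 x ULN; shift normal to high.
- Baseline as last value before the first OLE dose: 2.0 - 2.0 = 0; high to high.

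If this patient's repeat dosing starts in the OLE, the repeat-dosing baseline gives the second answer. The two baselines then precede the same dose but differ.

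**5. Effect on shift counts.** One patient whose category changed between the studies and stayed changed adds 1/50 = 2.0 percentage points if all of about 50 patients are in one dose group, or 1/25 = 4.0 points if two groups are split equally. These are the weight of one patient and do not estimate an effect.

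As an illustration, assume a proportion q of 50 patients changes category for one analyte in the gap and stays changed:

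| Assumed q | Expected extra shifts, 50q | Chance of at least one, 1 - (1 - q)^50 |
|---|---|---|
| 2% | 1.0 | 63.6% |
| 5% | 2.5 | 92.3% |
| 10% | 5.0 | 99.5% |

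With the last value before the first OLE dose as baseline, these particular shifts number zero. The documents give no basis for choosing q.

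**The case against.** The best defence is that the sentence is loosely drafted and not a deliberate rule. It says *generally*, which leaves room for exceptions. Patients must also have completed a late parent-study visit before entry, so a parent value would ordinarily precede the first OLE dose anyway. The closing limit in the sentence does little unless later pre-dose values were in mind. This stands as a comment on intent, and the point is therefore put as a literal reading. But no exception is named, and the neighbouring bullet shows that the plan could state a baseline without tying it to one study.

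Second, neither the change summary nor the shift summary names its baseline. This also stands: the consequence holds only where the OLE baseline is the one used.

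Third, by-visit results would show the Week 1 values, so an attentive reader could see the earlier movement. That softens the effect but does not correct the change or shift columns.

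A reader might infer more than the documents support:

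- *That the laboratory safety endpoint is compromised.* Section 4.3 concerns clinically significant changes. Under Section 8.1 that is the investigator's judgment, recorded as adverse events, and it is not calculated from this baseline.
- *That exclusion 7a contradicts the analysis.* It checks ALT and AST "values at Screening or Baseline >3 times the upper limit of normal (ULN"). An eligibility time point can share a name with a different analysis baseline; this is inconsistent terminology only.
- *That the mixed models in Section 10.4.4 are biased.* That section refers only to a relevant baseline, and the rules in 10.4.2 are for safety analyses. The term is undefined there, but no error follows.

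**Conclusion.** The point holds as a wording defect with a real but bounded consequence. On a literal reading, the OLE baseline bypasses central laboratory values that the schedule collects before the first OLE dose. Movement in that interval then counts as post-baseline change in any change or shift summary that uses the OLE baseline.

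The size is unknown and is zero if nothing moved. The roughly 8 weeks is a maximum for one case, not an expected gap. The 2.0 and 4.0 points assume 50 patients enrolled, an equal split for the second figure, and the dose group's safety population as denominator.

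The effect is limited to descriptive central-laboratory summaries, and to ECG change where a new Screening ECG exists. Tables of TEAEs, serious TEAEs and discontinuations, and listings of clinically significant laboratory findings, do not depend on this baseline. Nor should the extra movement be called untreated change: for patients given active drug in the parent study, it is only change before the first OLE dose. The correction is worth making because it is nearly free and bears on the primary objective, but the wording does not invalidate the safety analysis.

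**What to change.** Replace the OLE baseline bullet in Section 10.4.2 with: *The OLE baseline is the last non-missing value before the first dose in WVE-HDSNP1-002, whether collected in WVE-HDSNP1-001 or at OLE Screening/Day 1 pre-dose.* Make clear that a Week 1 sample drawn up to 1 week ahead under footnote f counts as pre-dose. Parent values remain the baseline where nothing newer exists, so no patient loses a baseline.

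In the same section, state which baseline the OLE-only and the integrated change and shift summaries each use.

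Optionally, name the baseline for each mixed model in Section 10.4.4 (OLE baseline for the OLE-only model, repeat-dosing baseline for the integrated one). This is a clarification and not part of the error.

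The cost is a few sentences and the matching baseline derivation. No new data are needed, and no sample size figure changes.

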Based on the SMC and DEC review of Phase 1b/2a safety data, the highest tolerated dose level and/or a lower dose level may be selected for multiple dosing and further evaluation in the OLE. If one dose level is selected, all patients will be switched to receive treatment at that dose level. If more than one dose is selected, patients will be randomized 1:1 to the highest tolerated dose and one lower dose to be determined by the DEC in agreement with the SMC. The randomization will be stratified by cohort and use a fixed block size. These doses may be further revised based on emerging safety, PD, or clinical effects data in the Phase 1b/2a study. The maximum dose and frequency in this OLE study will not exceed the maximum dose and frequency described in the Phase 1b/2a protocol (WVE-HDSNP1-001) approved in each country. For more details on additional dose modifications refer to [Section 4.1](#).

At the time when the Phase 1b/2a study is completed, the dose and dose interval in this OLE study may be further adjusted. A final determination about the optimal dose and dose-frequency will be made on the basis of data from the WVE-HDSNP1-001 study. It is possible that patients will be up-titrated or down-titrated depending on the dose they were receiving at the time of that decision. Up- or down-titration of the dose will only occur at the cohort level, not on an individual patient level.

The follow-up period will continue to Week 101, 4 weeks after the last dose. Based on PK data from animal studies, the plasma half-life of WVE-120101 is less than 24 hours and the potential for accumulation is low. Clinical data from the ongoing WVE-HDSNP1-001 study show that adverse events tend to occur within the first week or two after dosing. A 4-week follow-up period after the last dose is therefore considered a sufficient period of time to observe potential adverse events.

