4.1.4 Early Treatment Withdrawal and Early Termination

If a patient withdraws from treatment, but wishes to remain in the study, the patient should continue with all planned visits and applicable assessments. PK assessments as well as lumbar punctures (with associated labs) will no longer be necessary unless a patient agrees to allow for one final lumbar puncture. A urine pregnancy test should be completed on the visit after the last dose of treatment.

If a patient withdraws from the study, the patient should complete an early termination visit ([Table 1](#)).

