5.2.1.1 Non-Childbearing Potential

Non-childbearing potential is defined as a female who meets either of the following criteria:

- Postmenopausal state defined as no menses for 12 months without an alternative medical cause, or
- Documented hysterectomy, bilateral tubal ligation, or bilateral oophorectomy

5.2.1.2 *Highly Effective Methods of Contraception*

Contraception methods that can achieve a failure rate of <1% per year when used consistently and correctly are considered highly effective birth control methods. Such methods are defined as one of the following:

- True abstinence, defined as refraining from heterosexual intercourse for the duration of the study, when in line with the preferred and usual lifestyle of the subject
- Vasectomized partner (if that vasectomized partner is the sole sexual partner and has received medical assessment of the surgical success of the vasectomy)
- An intrauterine hormone-releasing system (IUS)
- Combined (estrogen and progesterone containing) hormonal contraception associated with inhibition of ovulation (oral, intravaginal or transdermal combined)
- Progesterone-only hormonal contraception associated with inhibition of ovulation (oral, injectable, or implantable)
- An intrauterine device (IUD)

Note that periodic abstinence (calendar, symptothermal, post-ovulation methods), withdrawal (coitus interruptus), spermicides only, and lactational amenorrhoea are not acceptable methods of contraception.

5.3 **Withdrawal and Discontinuation**

Patients are free to withdraw from the study or discontinue study treatment at any time upon request without prejudice to their future medical care by the Investigator or at the study site. Patient participation in the study may also be stopped at any time at the discretion of the Investigator or at the request of the Sponsor, as described in [Section 5.3.1](#). Patients who withdraw or discontinue from study treatment will no longer receive investigational drug.

5.3.1 ***Withdrawal of Patient from the Study***

Patients must be withdrawn from the study for any of the following:

- The patient withdraws consent
-

- At the discretion of the Investigator for medical reasons
- At the discretion of the Investigator or Sponsor for noncompliance
- Significant protocol deviation
- Termination of the study by the Sponsor (See [Section 14.4](#) for additional details)

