5.3.2 Discontinuation of Study Treatment

A patient may permanently discontinue study treatment for any of the following:

- The patient is withdrawn from the study ([Section 5.3](#))
- The patient experiences a serious or intolerable AE that in the Investigator's opinion requires treatment discontinuation
- A change in the patient's medical condition not consistent with the protocol requirements or that justifies withdrawal from the study or study drug
- Pregnancy (refer to [Section 9.5](#))

If a patient discontinues treatment, they will be encouraged to remain in the study to be monitored and complete applicable study related procedures (see [Section 4.1.4](#) for more details), unless consent is withdrawn. Patients who discontinue treatment due to an AE ([Section 9](#)) or pregnancy ([Section 9.5](#)) may require longer follow-up.

The reason for discontinuation of study treatment must be recorded in the eCRF and source documentation.

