9 ADVERSE EVENTS

The Investigator is responsible for reporting all AEs that are observed or reported during the study, regardless of their relationship to study treatment or their clinical significance.

Adverse event information will be collected beginning at enrollment (date of signed informed consent) and up to the end of the study. All ongoing AEs at the end of the study will be followed to resolution, or until the Investigator and the Sponsor agree that further follow-up is not required.

An AE is defined as any untoward medical occurrence in a patient enrolled into this study regardless of its causal relationship to study treatment. Patients will be instructed to contact the Investigator at any time after Screening if any symptoms develop.

A TEAE is defined as any event not present before exposure to study treatment or any event already present that worsens in either severity or frequency after exposure to study treatment.

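### The on-treatment AE window in Section 10.4.2 stays open to the end of the study, so AEs arising after a patient has stopped drug are not separated from AEs on drug in the TEAE tables

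*Combined protocol and SAP*

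**What the plan says.** Section 10.4.2 sets the AE observation periods for the safety analysis. For the extension, "OLE on-treatment adverse events are AEs that developed or worsened from the first dose of study drug in the OLE to study completion/discontinuation", and "Summaries of TEAEs will include all OLE on-treatment AEs". The parallel definition for integrated data ends the same way: "Repeat dosing on-treatment adverse events are AEs that developed or worsened from the first dose of repeat dosing to study completion/discontinuation". The only other period defined there is the pre-OLE one, from consent to first OLE dose. The general definition in Section 9 has a start but no end: "A TEAE is defined as any event not present before exposure to study treatment", or one already present that worsens after exposure.

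Stopping drug and leaving the study are separate events in this protocol. Section 5.3 says "Patients who withdraw or discontinue from study treatment will no longer receive investigational drug". Section 5.3.2 adds: "If a patient discontinues treatment, they will be encouraged to remain in the study to be monitored". Section 4.1.4 then says: "If a patient withdraws from treatment, but wishes to remain in the study, the patient should continue with all planned visits and applicable assessments". The planned visits run to Week 101 (Section 4.1.3), and AEs are collected to the end of the study (Section 9).

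On how long to watch after a dose, Section 2.1 reports that AEs tend to appear in the first one or two weeks, and concludes: "A 4-week follow-up period after the last dose is therefore considered a sufficient period of time to observe potential adverse events".

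**The concern.** A patient who completes dosing is observed for about 4 weeks after the last dose. A patient who stops early and stays is observed for much longer without drug, and every AE in that time is still labelled on-treatment and reported under a dose group.

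This matters because long-term safety and tolerability is the primary objective (Section 3) and the disease is progressive (Section 1.1). AEs that reflect disease progression are recorded (Section 9.1), and Section 9.3.2 gives a disease flare that leads to hospitalisation as an example of an SAE. Such events can accrue in undosed patients. They would raise the TEAE and serious TEAE counts, and no planned table would show how many arose off drug.

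**Working it through.** The plan states no sample size calculation, discontinuation rate or event rate, so there is no figure of its own to reproduce. What can be checked is the schedule arithmetic and the size of the effect under stated assumptions.

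**Inputs from the documents.** Dosing is every 4 weeks from Week 1 to Week 97 (Sections 4.1 and 6.2.2), that is (97 − 1)/4 + 1 = 25 doses. Follow-up ends at Week 101, and 101 − 97 = 4 weeks, which agrees with Section 4.1.3. About 50 patients are planned (Section 5). AE percentages use the safety population of each dose group as denominator (Section 10.4.2).

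**Assumptions.** A proportion d = 10-40% stops drug early. The last dose is spread evenly over doses 1 to 24. A proportion s = 50% or 100% of stoppers stays to Week 101, and the rest leave 4 weeks after their last dose. The background AE is unrelated to drug and has a constant rate.

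**Step 1: one patient who stays.** Weeks labelled on-treatment but more than 4 weeks after the last dose = 101 − (w + 4), where w is the week of the last dose.

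| Last dose | Weeks beyond last dose + 4, of 100 |
|---|---|
| Week 1 | 96 |
| Week 25 | 72 |
| Week 49 | 48 |
| Week 73 | 24 |
| Week 97 (completer) | 0 |

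Averaged over doses 1 to 24 this is 50 weeks per stopper who stays.

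**Step 2: share of labelled time across 50 patients.** Off-drug patient-weeks = 50 × d × s × 50. Patient-weeks up to last dose + 4 = 50 × (1 − d) × 100 + 50 × d × 50. For d = 10% and s = 50%: 125 / (125 + 4,750) = 2.6%. For d = 40% and s = 100%: 1,000 / (1,000 + 4,000) = 20.0%.

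| Stop early | Half stay | All stay |
|---|---|---|
| 10% | 2.6% | 5.0% |
| 20% | 5.3% | 10.0% |
| 30% | 8.1% | 15.0% |
| 40% | 11.1% | 20.0% |

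**Step 3: effect on a per-patient incidence.** P(at least one event) = 1 − exp(−rate × weeks/52). At an assumed 0.3 per patient-year, over 100 weeks: 1 − exp(−0.3 × 100/52) = 43.8%. For stoppers counted only to last dose + 4 weeks, the average over windows of 4, 8, …, 96 weeks is 24.1%. Cohort incidence with the earlier end, all stoppers staying, is (1 − d) × 43.8% + d × 24.1%:

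| Stop early | To study end | To last dose + 4 weeks | Difference, patients of 50 |
|---|---|---|---|
| 10% | 43.8% | 41.9% | 1.0 |
| 20% | 43.8% | 39.9% | 2.0 |
| 30% | 43.8% | 37.9% | 3.0 |
| 40% | 43.8% | 35.9% | 3.9 |

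The difference equals d × s × (43.8% − 24.1%). It halves if half of the stoppers stay (about 0.5 to 2 patients) and is zero if none do. At an assumed 0.1 per patient-year with all staying it is 0.4 to 1.7 patients of 50; at 1.0 per patient-year, 1.5 to 5.9.

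**Step 4: last visit of a completer.** Table 1 gives the Week 97 and Week 101 visits a window of ±1 week each. The longest interval from last dose to last visit within the windows is 4 + 1 + 1 = 6 weeks, so a cut-off at exactly 4 weeks, or at 5, could move some completers' final-visit AEs out of the on-treatment table.

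**The case against.** The strongest reply is that counting every AE after the first dose agrees with the Section 9 definition and is the cautious choice for an uncontrolled study of an intrathecal antisense drug. Section 1.3 says the potential duration of knockdown is unknown, and Section 5.3.2 foresees longer follow-up for some patients who stop because of an AE. This stands. It is the reason to keep the all-study table, but not a reason to leave off-drug events unseparated.

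Some mitigation also stands. AE onset dates and action taken with drug are recorded (Section 9.1). Tables by relationship and listings of all AEs are planned, and a repeated event counts once per patient (Section 10.4.2). Worsening seen only on the clinical rating scales is not an AE (Section 9.1). A reader could reconstruct the split from the listings, but no planned summary makes it.

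Several stronger readings are tempting, and the documents do not support them:

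- A reader might infer that off-drug time is counted as drug exposure. It is not: exposure has its own summary (Section 10.4.1), AE denominators are patients, and no rate per unit of time is planned that could be diluted.
- A reader might infer that stoppers are held in the study. Staying is voluntary, and for those who leave, the window closes at that point.
- A reader might treat the 4 weeks in Section 2.1 as an attribution rule. That text justifies the length of follow-up after the final dose. It makes 4 weeks a natural choice, not one already made.
- A reader might judge the tables by one early stopper. A patient whose last dose is at Week 9 and who stays has 88 of 100 weeks beyond the 4-week point, but that is close to the extreme case; the table-level effect is a few patients.
- A reader might add that the repeat-dosing window spans an undosed gap between the two studies. AE collection in the parent study is not described here, and events that are not collected cannot inflate a table.

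**Conclusion.** The point holds as one of labelling and separation. As written, Section 10.4.2 classes AEs in undosed patients as on-treatment and reports them under a dose group in tables that serve the primary objective, with no post-treatment period in either the OLE or the repeat-dosing analysis. That much follows from the text alone.

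The size depends on assumptions. It ranges from nil, if stoppers leave the study, to about 20% of labelled time and about 4 of 50 patients for an event at 0.3 per patient-year, if 40% stop at evenly spread times and all stay. Since no stopping or retention rate is given, the actual figure cannot be derived. The change is worth making before the tables are produced, because it is cheap and loses no event.

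**What to change.** In Section 10.4.2:

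- Split OLE TEAEs by time since last dose. On-treatment would run from first OLE dose to last dose plus 4 weeks, with a margin that covers both 1-week visit windows, so up to 6 weeks. Later events would be post-treatment follow-up, tabulated by last dose received.
- Keep the TEAE table to study end, so that a late-onset effect remains visible.
- Apply the same end to the repeat-dosing window.

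Because denominators are patients, a shorter window lowers the percentages in a dose group with more early stoppers. The on-treatment table should therefore be read with the exposure summary of Section 10.4.1, or exposure-adjusted rates added.

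The cost is a wording change and one extra set of AE tables, built from dosing and AE-onset dates already collected. The downside is that a true late effect would appear in the follow-up and all-study tables rather than the on-treatment table.
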